### B1. PURPOSE OF PROTOCOL

#### **Purpose**

We recently completed a 35-week double-blind, placebo-controlled, crossover study investigating weight loss with exenatide treatment in a group of 41 overweight and obese women without diabetes. We found that a subset of women, approximately 30%, lost 5-13% of their body weight during the exenatide treatment period (average weight loss 8% at 16 weeks). We designated this subgroup "high responders." We found that weight loss with exenatide treatment could be identified as early as 4 weeks and continued throughout the 16 week treatment period.

We are now conducting a followup study that will investigate the possible mechanisms of weight loss associated with exenatide treatment and the metabolic characteristics of high responders to exenatide treatment. We will also examine the magnitude and duration of weight loss among a cohort of high responders over 52 weeks of treatment, and at 3 and 6 months following treatment.

#### *Hypothesis:*

The mechanisms of weight loss with exenatide are not fully understood, and weight loss responses to exenatide are highly variable, possibly reflecting distinct metabolic parameters. By identifying and following a group of obese women who lose  $\geq 5\%$  body weight after short-term exenatide treatment, we can gain insights into the possible mechanisms of weight loss and assess long-term weight loss with this pharmacotherapeutic intervention.

#### **Primary Outcomes**

The primary objectives of this study are:

1. To investigate possible mechanisms of weight loss with exenatide treatment
2. To determine long-term patterns of weight loss among individuals who have robust (>5%) early weight loss with exenatide

#### **Secondary Outcomes**

Our secondary objective is to identify metabolic characteristics that predict robust response to exenatide treatment.

#### *Outcome measurements:*

*Weight:* We will compare the duration and magnitude of weight loss among exenatide responders with the

duration and magnitude of weight loss among subjects assigned to placebo with a calorie-restricted diet over 52 weeks. We will also compare changes in weight at 3 and 6 months after the cessation of exenatide treatment or diet. Weight loss will be correlated to baseline BMI.

**Body composition:** Baseline body composition may predict response to exenatide treatment, and weight loss with exenatide may be associated with decreased fat versus lean body mass compared to diet-induced weight loss. We will compare the effect of exenatide treatment versus caloric reduction on body composition over 52 weeks using bioelectrical impedance analysis (BIA) and by measuring waist circumference.

**Resting energy expenditure (REE):** Our initial data suggest that exenatide may blunt the decrease in resting energy expenditure that is typically associated with diet-induced weight loss. We will measure resting energy expenditure (REE) via indirect calorimetry at baseline, at weeks 12, 24, and 52, and after 5%, 10%, 15% weight loss is achieved, and at additional 5% weight loss timepoints, as applicable (i.e., 20%, 25%, etc).

**Mixed meal test:** Exenatide may improve beta cell function and lower postprandial triglycerides in nondiabetic individuals. Measurement of fasting insulin and triglyceride levels does not capture these effects. We will administer a mixed liquid meal (Boost) and measure serial postprandial insulin, , and triglyceride levels. Subjects will have a mixed meal test at baseline, and at weeks 12, 24, and 52.

**Thermic effect of food:** Exenatide treatment may result in an increase in the thermic effect of food, which could explain, at least in part, why we did not see a significant reduction in energy expenditure among exenatide high responders in our initial study. We will measure the thermic effect of food using indirect calorimetry following the mixed meal challenge. Energy expenditure will be measured for 15-20 minutes every hour for four hours after the mixed meal challenge. The thermic effect of food will be measured in a subset of subjects at baseline, and at weeks 12, 24, and 52.

**Serum metabolic parameters:** Subjects will have blood drawn to measure leptin, soluble leptin receptor, insulin, cortisol, adiponectin, CRP, and FGF21. Blood will also be banked to measure other metabolic parameters in the future. Serum metabolic parameters will be measured at baseline and at weeks 12, 24, and 52. Serum metabolic parameters will also be measured when weight loss at a 5% increment has been achieved, or upon study completion if weight loss targets are not achieved.

**Hunger/Nausea/Satiety visual analog scales (VAS):** Perceptions of hunger, nausea or satiety early during exenatide treatment may predict and/or explain weight loss response. We will assess hunger, nausea and satiety at each study visit using standard 10cm horizontal visual analog scales.

**Physical activity monitoring with Actigraph accelerometers:** Subjects may be given wrist-worn accelerometers (Actigraph, MiniMitter) at week 0 to measure baseline physical activity levels. The will allow us to compare and control for baseline physical activity level differences between the placebo and exenatide groups. Subjects may be asked to wear the monitors again at study week 12, at study week 24, and after achieving 5%, 10%, 15%, weight loss, or weight loss > 15% at a 5% increment.

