## **B. Statistical Considerations**

### *Statistical methods:*

For the first objective of this study, we will examine the patterns of weight loss (termed “trajectories”) for the subjects with robust weight loss in the exenatide group (A), and also those in diet-induced weight loss group (B). We expect to see that in group A, the trajectory of weight loss for the majority of subjects will be consisted of 2 linear segments (T1). The first segment starting at week 12 will have a steeper negative slope (rate of weight loss decrease) than that of the second linear segment, which would have a less steep slope and plateau out toward week 52. However, individual subjects are expected to follow different trajectories. For example, some may have a constant gradual negative slope from week 12 to week 52 (one single linear segment), some may have three segments (plateau at first, then decrease, then plateau), and some may have no change at all after week 12 (one single plateau). The trajectory analysis will allow us to first assess the number of possible trajectories, and second, the shapes of the trajectories of weight loss. We are most interested in trajectory T1 which would allow us to estimate not just the rate of change over time for each of the two linear segments, but also the duration of time for each of the two segments.

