**Sample size calculation:**

Based on published literature describing weight loss with exenatide treatment among individuals with type 2 diabetes, we hypothesize that responders will stratify into a plateau group and a continued weight loss group by 52 weeks of treatment. The sample size is based on the difference between two differences of weight. The first difference is the weight difference between week 12 and week 52 for the exenatide group (group A), and the second difference is the difference between week 12 and week 52 for the diet-induced group (group B). The difference in weight loss between these two groups is hypothesized to be 1 kg (i.e. the exenatide group between week 12 and 52 loses on the average 1 kg more than group B). The common standard deviation of the distribution of the weight loss difference is 1.2 kg. We plan to enroll 150 subjects in group A and 36 in group B. Given an expected dropout rate of 25% from the screening visit, we will screen 200 for group A, and 50 for group B. At 12 weeks, we expect that 30% of group A will be high responders (50 subjects). At 52 weeks, we expect the dropout rate to be 25% for group A and 50% for group B. Thus we will have 38 subjects left for group A, and 18 for group B for final data analysis. Given this sample size, we will still have a power of 0.83 to detect the difference of 1kg.

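### The weight comparison is described over 52 weeks in one section and powered from week 12 to week 52 in another; the two can differ, possibly in sign, and neither is named primary

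*Combined protocol and SAP*

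**What the plan says.** All references are to the combined protocol and SAP.

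- **B1, Primary Outcomes.** The weight objective is "To determine long-term patterns of weight loss among individuals who have robust (>5%) early weight loss with exenatide". It gives no variable, time origin or comparator.
- **B1, Outcome measurements, Weight.** Loss in women who respond to exenatide is to be set against the "duration and magnitude of weight loss among subjects assigned to placebo with a calorie-restricted diet over 52 weeks". The exenatide side is restricted to responders; the placebo side is everyone assigned. No starting point is named, but a 52-week period in a 52-week trial is naturally read from week 0.
- **B3.B, Statistical methods, first objective.** Trajectories are examined "for the subjects with robust weight loss in the exenatide group (A), and also those in diet-induced weight loss group (B". For the expected main pattern, "The first segment starting at week 12 will have a steeper negative slope".
- **B3.B, Statistical methods, aim 2.** The binary outcome is a loss of at least 1 kg between weeks 12 and 52.
- **B3.B, Sample size calculation.** "The first difference is the weight difference between week 12 and week 52 for the exenatide group (group A"; the "second difference is the difference between week 12 and week 52 for the diet-induced group (group B". The target difference is 1 kg, the SD 1.2 kg, the analysed numbers 38 and 18, and the power 0.83.
- **B3.A, Overview, Rationale for study design and Study duration.** Women in either arm with less than 5% loss at week 12 leave the study. Placebo women with less than 10% loss at week 24 also leave. Exenatide responders stay even if weight plateaus or is regained.

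**The concern.** Two elements of one comparison differ between sections.

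**Window.** B1 speaks of magnitude and duration over 52 weeks. The sample size and aim 2 count only what happens after week 12, which leaves out the period in which the loss that defines a responder occurs. An advantage confined to weeks 12-52 is not the same finding as greater weight loss over the year. Investigators are not blinded, and without a named primary variable the window could be chosen after the results are known.

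**Population.** Read literally, B1 selects the exenatide arm on early weight loss and leaves the placebo arm unselected. A comparison built that way favours exenatide even if the treatments are identical. The sample size section does not settle who is in group B: group A has an explicit responder step at week 12, while group B goes from 36 to 18 through 50% dropout alone.

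**Working it through.** **1. The plan's own power figure.** Inputs from the sample size calculation: difference 1 kg, SD 1.2 kg, n = 38 and 18. Two-sided alpha of 0.05 is my assumption; that section states none.

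- SE = 1.2 × √(1/38 + 1/18) = 0.343 kg.
- Power ≈ Φ(1/0.343 − 1.96) = Φ(0.95) = 0.83. The stated figure reproduces (0.830 by normal approximation; 0.816 by noncentral t).

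The 1.2 kg is the SD of the week 12-52 change. The documents give no SD for the 0-52 change, so 0.83 does not carry over to the B1 comparison. With 38 v 18, a 1 kg difference and assumed SDs for the 0-52 change, power (two-sided t) is 0.40 at 2 kg, 0.21 at 3 kg, 0.14 at 4 kg and 0.09 at 6 kg.

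**2. How the two windows relate.** For the same women:

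(A−B over 0-52) = (A−B over 0-12) + (A−B over 12-52).

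Set the last term to the hypothesised +1 kg in favour of exenatide (A). The first column is assumed.

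| A−B in loss at week 12 | A−B over 12-52 | A−B over 0-52 |
|---|---|---|
| 0 kg | +1 | +1 |
| −1 kg | +1 | 0 |
| −2 kg | +1 | −1 |

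For example, exenatide losing 7 kg then 3 kg and diet losing 8 kg then 2 kg gives +1 kg over weeks 12-52 and 10 − 10 = 0 over 0-52.

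**3. The literal comparator, at week 12.** Assume identical arms, normally distributed percentage loss at week 12, and a proportion p reaching 5%. Responders then exceed all assigned women by SD × φ(z)/p, with z = Φ⁻¹(1 − p). For p = 0.6 (the approximate exenatide responder rate in the Rationale, here applied to both arms), φ(z)/p = 0.644. The gap is 1.9, 2.6 or 3.2 percentage points for assumed SDs of 3, 4 or 5. At an assumed 95 kg that runs from 0.95 × 1.93 = 1.8 kg to 0.95 × 3.22 = 3.1 kg. At p = 0.3 it is 3.5 to 5.8 points. These figures describe loss **to week 12**.

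**4. What the retention rules do by week 52.** I simulated identical arms under these assumptions: 100 kg women; week-12 loss mean 4 or 5 kg, SD 4; later loss mean 2 kg, SD 4, linear over weeks 12-52; correlation between early and later loss −0.3, 0 or 0.3. Both arms were cut at 5% at week 12, and placebo alone at 10% at week 24. By week 24, 12/40 = 0.3 of the later loss has occurred.

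- With the week-12 rule alone in both arms, the 12-52 contrast is about 0.
- With the week-24 rule added, among women still in the study at week 52, the 12-52 contrast favours **placebo** by about 1.0 to 2.4 kg. For instance, with mean 5 kg and correlation 0, mean later loss is 2.01 kg on exenatide and 3.80 kg on placebo, a gap of 1.79 kg.
- The 0-52 contrast in the same women favours placebo by about 4.1 to 5.1 kg.

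**The case against.** The strongest reply is that B1 is an overview of measurements. It uses the same 52-week phrase for body composition and names no baseline. The statistical section supplies the specific contrast, and a post-week-12 change suits an objective about long-term pattern after an early response. On population, the Overview, Rationale, Study duration and Study Visits all remove placebo women under 5% at week 12, and the Rationale calls the diet arm a weight-loss comparison group. Those women have no planned weights after week 12, so a comparison of observed weights at week 52 cannot include them.

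Most of the population reply stands. A reader might infer from step 3 that the week-52 result would be inflated in favour of exenatide by 2 to 3 kg. The documents do not support that: the figure belongs to week 12 and should not be set against the 1 kg target for weeks 12-52. By week 52 the placebo women still in the study are the more heavily selected group, and the bias in observed data runs the other way.

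A reader might also infer that the two windows will give opposite answers. That too is unsupported, because no week-12 or 0-52 weights by arm are given. Nor does the trajectory text define a change score; it describes an expected shape fitted to monthly weights.

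The reply on window does not stand. B1 holds the only outcome definition for weight, it refers to magnitude over 52 weeks, and no section says that the week 12-52 change replaces it or that both will be reported.

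**Conclusion.** The inconsistency in window is real and unresolved. B1 gives loss over 52 weeks; the sample size calculation and aim 2 give the week 12-52 change; neither is named primary. The two contrasts differ by exactly the arm difference at week 12, so the hypothesised 1 kg advantage could be zero or reversed over the year if exenatide is 1 kg or more behind at that point. That follows from arithmetic; whether it will happen cannot be judged from the documents. The power of 0.83 is correct under the assumed two-sided 0.05, and it belongs to week 12-52 only.

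The one-sided responder condition in B1 is a defect of wording that matters mainly for weights up to week 12. At week 52 the larger problem is the placebo-only 10% rule. Under the assumptions of step 4, it biases completers-only contrasts toward placebo by about 1.0 to 2.4 kg (12-52) and 4.1 to 5.1 kg (0-52). The direction follows from the rule; the sizes depend on the assumed means, SDs and correlations. The plan should be changed, and the change is one of definition and analysis.

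**What to change.** Rewrite the B1 weight outcome and align the Statistical methods and Sample size calculation with it:

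- **(a) Population.** Define the women compared in both arms by the same week-12 rule of at least 5% loss, as the Overview already does.
- **(b) Powered outcome.** Name the week 12-52 change as the powered weight outcome.
- **(c) Companion estimate.** Report the week 0-52 change for the same women beside it, and do not claim greater total weight loss from the 12-52 result alone.
- **(d) Estimation.** Estimate both from a likelihood-based longitudinal model that includes every week-12 responder, with weights to week 24 from placebo women removed under the 10% rule. Do not rely on completers-only contrasts at week 52.

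The cost is protocol wording and slightly more analysis of weights already scheduled. No treatment or retention rule changes. There are three downsides. The model assumes data are missing at random after week 24; removal depends on a recorded weight, which helps, but under the rule no placebo woman below 10% at week 24 is followed later, so her course rests on the model. A less favourable 0-52 result must be reported if it arises. And the contrast remains one between women selected after randomisation, so it should not be presented as a randomised comparison.

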### **Delayed Gastric Emptying Substudy**

Delayed gastric emptying is a known effect of exenatide treatment. Delayed gastric emptying can cause early and prolonged satiety, both of which may contribute to exenatide-induced weight loss. There is no literature on the effect of delayed gastric emptying on energy expenditure, in particular the thermic effect of food. Preliminary data from this study indicate that exenatide treatment is associated with a blunting of the thermic effect of food. This blunting is seen among exenatide responders (> 5% weight loss after 3 months of treatment) and among nonresponders (< 5% weight loss at 3 months). In contrast, individuals assigned to the placebo group maintain a 100-300 calorie increase in resting energy expenditure (the thermic effect of food, TEF) even in the setting of weight loss comparable to exenatide responders.

These intriguing data are the rationale behind a substudy that will further examine the effect of delayed gastric emptying on TEF. This substudy will specifically examine the effect of low-dose morphine, an agent that also delays gastric emptying, on TEF. By studying another agent known to delay gastric emptying through a different pharmacologic mechanism, we can determine whether the blunted TEF that we see with exenatide is due to delayed gastric emptying or another mechanism of action of exenatide. For the substudy, we will recruit women who have completed treatment in the main study, either at 3 months (nonresponders) or at 12 months (responders). As mentioned, we have observed a blunting in TEF among both responders and nonresponders to exenatide, indicating that this effect is due to exenatide and independent of weight loss. Our current study population excludes women with diabetes or gastroparesis, both of which we also want to exclude in this substudy.

### **Study Population**

Our study population will be generally healthy, non-diabetic women age 18-70 years with BMI 28-50 kg/m^2.

## B2. SIGNIFICANCE AND BACKGROUND FOR THE STUDY

Incretin mimetics, medications that mimic the effects of incretin hormones produced by the L cells of the small intestine, are gaining popularity for the treatment of type 2 diabetes. Incretin mimetics are typically associated with more weight loss than any other class of antidiabetic agents. Exenatide, a glucagon-like peptide 1 (GLP-1) receptor agonist, was the first incretin mimetic approved in 2005. Liraglutide, a GLP-1 analog, was approved in 2010, and there are several additional incretin mimetics in development. Exenatide causes glucose dependent insulin secretion, restoration of the first phase insulin response, and reduction of postprandial glucagon secretion. Exenatide also causes delayed gastric emptying and decreases food intake through mechanisms that are not completely understood (Drucker et al., 2003; Iltz et al., 2006; Palamara et al., 2006). Exenatide is currently approved as a twice daily injection.

Exenatide is associated with weight loss among individuals with type 2 diabetes when used as monotherapy or in conjunction with metformin or a sulfonylurea (Buse 2004; DeFronzo 2005; Kendall 2005; Riddle 2006; Moretto 2008; Buse 2009). Exenatide and liraglutide have also been associated with weight loss among obese individuals without diabetes (Rosenstock 2010; Astrup 2010). Retrospective analysis has shown that weight loss is greater among diabetic individuals with BMI > 30 compared to those with BMI < 30, however there are no published prospective studies that have characterized individuals who have robust weight loss with exenatide. Similarly, there are no studies that have examined weight trajectories following termination of exenatide treatment among individuals without diabetes.

An important clinical consideration with all pharmacotherapeutic agents, and especially those that are associated with weight loss, is identifying as early as possible individuals who do and do not respond to treatment. In our recently completed study of 41 overweight and obese women without diabetes, we found that exenatide treatment was associated with a significant decrease in weight, BMI, and waist circumference compared to placebo. There was also a trend towards decreased sleep latency (how long it takes to fall asleep) with exenatide treatment compared to placebo. We did not find any significant differences in blood pressure, body composition, lipid parameters, leptin levels, insulin levels or resting energy expenditure when we compared exenatide treatment to placebo overall, but we did note that a few subjects had dramatic changes in fasting insulin, glucose, leptin, or triglyceride levels.

In our initial study we also made the interesting observation that exenatide high responders did not have a significant decrease in resting energy expenditure (REE) despite an average 8% weight loss. Whereas diet-induced weight loss of this magnitude has been shown to result in a decrease in resting energy expenditure, which facilitates weight regain, our data suggest that exenatide may blunt this decrease in REE and thereby permit ongoing weight loss. In the present study, we will compare resting energy expenditure as well as the thermic effect of food among exenatide high responders, nonresponders, and subjects with diet-induced weight loss.

Another mechanism of weight loss may be a change in leptin sensitivity. Serum leptin levels have been shown to fall in obese individuals with diet-induced weight loss (Crujeiras 2010), and in our initial study, we found that high responders had a significant decrease in leptin levels compared to nonresponders. While this decrease may reflect weight loss, it may also reflect sensitization to leptin. Furthermore, measurement of total serum leptin levels may not be the best tool for assessing leptin sensitivity. In a cohort of lean males fasted for 72 hours, leptin levels fell while levels of the soluble leptin receptor increased (Chan et al, 2002). Measurement of both total leptin and soluble leptin receptor levels, and in turn calculation of the free leptin index, can provide more a more detailed assessment of leptin resistance.

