**Study duration:**

All subjects randomized to exenatide treatment will continue participation for 12 weeks. At 12 weeks, subjects who are high responders will continue participation for 52 weeks plus followup visits at 3 and 6 months. Exenatide high responders will remain in the study even if weight loss plateaus or if there is weight regain. Exenatide nonresponders will discontinue participation after 12 weeks.

Subjects in the placebo/diet intervention arm will discontinue participation if they fail to lose 5% of their body weight after 12 weeks or 10% of their body weight after 24 weeks. Subjects who demonstrate ongoing weight loss will continue placebo/dietary intervention for up to 52 weeks, plus follow-up visits at 3 and 6 months. Metabolic monitoring will occur when subjects have lost 5% and 10% of their body weight.

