### Study Visits:

- **Screening visit**
  - Informed consent obtained in writing
  - Standard measurements (blood pressure, heart rate, height, weight, waist circumference, body composition)
  - Physical exam and medical history
  - 24h food recall
  - Fasting safety labs (CBC, metabolic panel, transaminases, lipid panel, lipase, TSH, A1c)
  - Urine pregnancy test for premenopausal women
- **Week 0—Enrollment and randomization visit**
  - **Start exenatide or placebo at 5 mcg twice daily dose**
  - Standard measurements
  - Dietary counseling
  - Visual analog scales (VAS) to measure nausea, satiety, hunger
  - 24h food recall
  - Resting energy expenditure using indirect calorimetry
  - Fasting leptin, soluble leptin receptor, insulin, cortisol, adiponectin, CRP, FGF21 (draw before meal test)
  - Mixed meal test with serial measurements of postprandial insulin, and triglyceride levels
  - Measurement of thermic effect of food (TEF) in subset of subjects
  - Distribute Actical physical activity monitor to subjects if device is available
  - Urine pregnancy test for premenopausal women
- **Week 2—Titration visit**
  - Titrate dose of exenatide or placebo to 10mcg twice daily
  - Standard measurements
  - Dietary counseling
  - VAS to measure nausea, satiety, hunger
  - 24-hr food recall
  - Assessment of symptoms, adverse events, and diet/medication compliance
  - Urine pregnancy test for premenopausal women
- **Weeks 4 & 8—Follow-up visits**
  - Standard measurements
  - Dietary counseling
  - VAS for nausea, satiety, hunger
  - 24-hr food recall
  - Assessment of symptoms, adverse events, and diet/medication compliance
  - If subject has attained 5% or 10% weight loss, follow “5% or 10% weight loss procedures”
  - Urine pregnancy test for premenopausal women
- **Week 12—Exenatide and placebo nonresponders (<5% weight loss) discontinue participation**
  - Fasting safety labs for all subjects (CBC, metabolic panel, transaminases, lipid panel, lipase)
  - Fasting leptin, soluble leptin receptor, insulin, cortisol, adiponectin, CRP, FGF21 levels
  - Standard measurements

- Physical exam
- Dietary Counseling
- VAS for nausea, satiety, hunger
- 24-hr food recall
- Assessment of symptoms, adverse events, and diet/medication compliance
- Resting energy expenditure
- Mixed meal test
- Thermic effect of food (TEF) in a subset of subjects
- Physical activity monitoring with Actical monitor if device is available
- Urine pregnancy test for premenopausal women
  

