To estimate the number and shape of the weight loss trajectories, we will use a mixture modeling technique of the longitudinal data of monthly weights for each subject. We will first plot the data for each subject over time. The graphs will allow us to have some understanding of the shape of the observed trajectories, and how the curves cluster. We will assume that the number of clusters ranges from one to six, but we expect the optimal estimate of the number of clusters is three or four, as described above, with the largest cluster consisting of trajectory of shape T1. The marginal density of a subject having weight measurement at a particular time point is modeled as a function of the product of two densities: the probability of the weight measurement belonging to a particular group, and the probability of observing such a measurement conditioning on the particular group. The first probability is modeled using a generalized logit model since the outcome is categorical (from 1 to 6 categories/types of trajectories), and the second probability is a polynomial linear regression of the weight measurement as a function of time (linear, quadratic, cubic). To select the optimal number of trajectories, we will compare the Bayesian Information Criteria (BIC) value from the six models (corresponding to 1 to 6 types of trajectories). The algorithm and the SAS macro for this type of modeling has been published (Jones 2007). We will repeat the modeling technique above for group B in order to assess the number and shapes of the trajectories in this group.

For aim 2, we will first create a binary outcome variable. The outcome is 1 if the weight loss difference between 12-week and 52-week is at least 1 kg; otherwise, it is 0. We will perform multivariable logistic regression to assess the association between metabolic parameters and this outcome. We consider the association to be statistically significant if the p-value is less than 0.05, and the overall model c-statistic is above 0.8. Once these metabolic parameters have been identified and quantified, we will also use the result from the trajectory analysis (aim 1) to assess the distribution of the metabolic parameters across different trajectories. We will model the likelihood of falling into a particular trajectory as a function of metabolic parameters (i.e. the change in a particular metabolic parameter may affect a certain trajectory but not all trajectories of weight loss).

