We will repeat these models for the subjects in group B. The difference in the estimates of the model coefficients between the two groups (A and B) implies the potential effect of exenatide.

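### Groups A and B are selected on weight loss after randomisation, so their difference cannot be read as an exenatide effect, and no arm-level week 0 to 12 analysis of the mechanism measures is prespecified

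*Combined protocol and SAP*

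**What the plan says.** B1, Primary Outcomes, puts first: "To investigate possible mechanisms of weight loss with exenatide treatment". B2 proposes to compare REE and the "thermic effect of food among exenatide high responders, nonresponders, and subjects with diet-induced weight loss".

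Two weight-loss rules decide who is followed. Study Visits, week 12, is headed: "Exenatide and placebo nonresponders (<5% weight loss) discontinue participation". Study duration says: "Subjects in the placebo/diet intervention arm will discontinue participation if they fail to lose 5% of their body weight after 12 weeks", and the same sentence adds a 10% requirement at week 24. That second rule applies to placebo only. Exenatide responders stay in even if they plateau or regain.

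Statistical methods (B3.B) models weight trajectories in group A (exenatide, robust loss) and group B (diet-induced loss). It then defines a binary outcome for a logistic model on metabolic parameters: "The outcome is 1 if the weight loss difference between 12-week and 52-week is at least 1 kg; otherwise, it is 0". The models are repeated for B, and the section concludes: "The difference in the estimates of the model coefficients between the two groups (A and B) implies the potential effect of exenatide". The Sample size calculation powers the A-minus-B difference in weight change from week 12 to week 52.

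Study Visits schedules REE, fasting hormones, the mixed meal test (insulin and triglycerides), body composition and the visual analogue scales (VAS) at weeks 0 and 12 in both arms. The thermic effect of food (TEF) is measured in a subset.

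**The concern.** Randomisation makes the two arms comparable at week 0. It does not make the women who lose 5% on exenatide with eucaloric advice comparable with the women who lose 5% on placebo with a 500-1000 cal/day deficit. One group is selected largely by response to a drug, the other largely by keeping to a diet. A difference in how metabolic parameters relate to later weight loss may therefore come from who passed in each arm.

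The week-24 rule adds an asymmetry. A placebo woman at 6% loss at week 12 must lose a further 4 percentage points by week 24 to stay. An exenatide woman at 6% may regain and still stay. This acts directly on the week 12 to 52 weight outcome.

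Meanwhile the contrast that randomisation does protect, apart from dropout, is not specified for the final data. That contrast is the two arms at week 12, before either rule removes anyone. The measures that bear on the first primary objective thus have no prespecified analysis by arm in the statistical section.

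**Working it through.** **1. The plan's own figure.** The Sample size calculation gives a difference of 1 kg, SD 1.2 kg, 38 v 18 women and power 0.83. Alpha is not stated there; two-sided 0.05 is assumed.
- Standard error = 1.2 × √(1/38 + 1/18) = 1.2 × 0.286 = 0.343 kg.
- Power = Φ(1/0.343 − 1.960) = Φ(0.952) = 0.83.

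The figure reproduces (0.816 with the noncentral t). It concerns only the selected groups and only weight.

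**2. Who is in each comparison.**

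| Comparison (section) | Measure | Selected on weight loss after randomisation? |
|---|---|---|
| Trajectories, A and B (Statistical methods) | Weight from week 12 | Yes, both groups |
| Logistic model, A then B (Statistical methods) | Further loss of at least 1 kg, weeks 12 to 52 | Yes; placebo also by the week-24 rule |
| Powered contrast, 38 v 18 (Sample size calculation) | Weight change, weeks 12 to 52 | Yes, as above |
| Responders, nonresponders, diet losers (B2) | REE, TEF | Exenatide arm split by outcome; diet arm limited to women with loss |
| Exenatide v caloric reduction (B1, Outcome measurements) | Body composition over 52 weeks | No limit in the sentence, but after week 12 only responders remain |
| 41 v 9 as randomised (B3.B, Delayed Gastric Emptying Substudy) | REE, TEF | No; preliminary, time point not stated |

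No section gives a model, test or population for a week 0 to 12 comparison by arm.

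**3. Possible size of the selection bias.** Assume a normal trait with no true arm difference and correlation r with week-12 loss, the same in both arms. If a fraction p passes the 5% rule, the passers' mean is r × φ(z)/p SD, where z cuts off the top p.
- p = 0.60: 0.3863/0.60 = 0.644
- p = 0.45: 0.3958/0.45 = 0.880
- p = 0.30: 0.3477/0.30 = 1.159

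The exenatide rate of about 60% is in Rationale for study design. The placebo rate is not given, so a range is shown:
- 60% v 30%: r × 0.515, or 0.10 SD (r = 0.2) to 0.36 SD (r = 0.7)
- 60% v 45%: r × 0.236, or 0.05 to 0.17 SD
- 60% v 60%: 0

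The zero holds only if the same trait acts equally strongly in both arms. The different treatments give no reason to expect that. The week-24 rule is not included.

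**4. What a comparison by arm could detect.** If the two counts in Rationale for study design add, enrolment to 6/5/15 was 84 + 24 = 108 exenatide and 28 + 10 = 38 placebo. At 80% power and two-sided 0.05, the detectable difference is 2.802 × √(1/n₁ + 1/n₂) SD.
- 108 v 38: 2.802 × 0.189 = 0.53 SD
- 81 v 28 (assumed 25% loss by week 12): 2.802 × 0.219 = 0.61 SD

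This is before any gain from baseline adjustment. It does not apply to TEF, whose subset size is not stated.

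**The case against.** The strongest defence is the design's purpose. Rationale for study design says the placebo arm exists to show metabolic changes due to weight loss without exenatide, and that the primary objectives need controls who lose at least 5%. A comparison by arm mixes drug, prescribed diet and unequal weight loss, so it does not isolate mechanism. This stands. It is why the comparison belongs beside the planned ones; making it the lead analysis would be a debatable change of estimand. It does not rescue a causal reading of A against B, which has the same diet difference plus selection.

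Three stronger readings are tempting, and the documents do not support them.
- A reader might infer that the mechanism data are never analysed by arm. The substudy section reports REE and TEF for 41 v 9 as randomised, and Outcome measurements plans an exenatide v caloric reduction comparison of body composition. The supportable statement is that no such week 0 to 12 analysis is prespecified in the statistical section.
- A reader might infer that the sentence on coefficients turns a mean difference in REE or TEF into a drug effect. It concerns the weight models. B2, which does compare REE and TEF, keeps exenatide nonresponders as a stratum.
- A reader might infer a precision gain by setting 108 v 38 against 38 v 18. The first is actual enrolment for a week-12 comparison, the second planned week-52 completers for another outcome. They are not like for like.

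The word potential in the plan's sentence is a hedge, but it still attributes the difference to exenatide.

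Nor is the comparison by arm free of every selection. Rationale for study design reports more exenatide dropout than expected, and the TEF subset has no stated selection rule.

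**Conclusion.** The point holds on two counts. First, A-versus-B differences come from groups formed by weight loss after randomisation: 5% at week 12 in both arms, plus 10% at week 24 in placebo only. They cannot be read as an effect of exenatide. Second, the statistical section specifies no comparison by arm of the week-12 mechanism measures, although the visit schedule collects them in both arms.

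The size of the bias cannot be fixed from the documents. The range of 0 to about 0.36 SD rests on a normal trait, an equal correlation of 0.2 to 0.7 in both arms and placebo pass rates between 30% and 60%. Rationale for study design calls the placebo response high, so the gap in pass rates may be small. The stated power of 0.83 is arithmetically sound and is not affected.

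**What to change.** 1. Prespecify, alongside the responder, nonresponder and diet-loser comparisons, a comparison by randomised arm of week-12 REE, mixed-meal insulin and triglycerides, fasting hormones, body composition, VAS and (in the subset) TEF. Include all randomised women whatever their weight loss.
2. Adjust for the week-0 value and for allocation period (3:1, 1:1, 2:1), because the arm proportions change with calendar time.
3. Add a sensitivity analysis for missing week-12 visits, and state how the TEF subset was chosen.
4. Reword the closing sentence of Statistical methods so that differences between responder-selected groups are called associations.

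The cost is wording and a few models on data already scheduled. The limits should be stated with the result. It is at 12 weeks, it estimates exenatide with eucaloric advice against placebo with calorie restriction, it is not matched on weight loss, and for TEF it covers only a subset.
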